## 9.6 Point of enrolment

Once patient has consented to take part in the study, they will be assigned a unique patient identification number via online platform Castor EDC (Ciwit B.V.), an electronic data capture system. All participants will be anonymised when registered onto Castor. The patient identification number is comprised of a five-digit number starting with a two-digit site number assigned by the co-ordinating centre, followed by a three-digit patient number, assigned chronologically for the entire study. For example, at site 01, the first patient enrolled will receive the number 01001. Each investigation site shall maintain a subject identification log of all the subjects enrolled in the clinical investigation. If the patient does not pass the screening assessments and is deemed ineligible to participate in the study, the patient will be considered a screening failure and is recorded as a screening failure in the subject identification and enrolment log. The patient identification numbers for screen failures are not to be re-used.

Once the patient has been consented to the study, the screening assessments as detailed in section 7.4.1 will be required to ensure patients eligibility:

## 9.7 Total expected duration of the clinical investigation

The investigation will last for 10 years from the date of surgery.

## 9.8 Subject duration and number

A total number of 250 cases will be recruited into the study for the duration of 10 years from date of surgery.

## 9.9 Enrolment Period

Cohort 1A will be recruited within 6 months of investigation start date.

Cohort 1B will be recruited within 6 months of investigation resumption date.

Cohort 2 (pre-upgrade) will be recruited within 1 year of local site approval.

Cohort 2 (post-upgrade) will be recruited within 1 year of local site approval or within 1 year of the clinical trial restart after design upgrade, whichever is longer.

# 10 Statistical Methods

## **10.1** Hypotheses and Sample Size

#### 10.1.1 Primary Objective - Safety and Efficacy Study

A total of 250 cases will be enrolled into the study at the 9 investigation sites.

When 250 cases are enrolled from all sites, enrolment will be stopped, regardless of the number contributed from each site.

The sample size is calculated based on the non-inferiority of the study device; the following hypotheses will be tested to test the difference in success rate (defined in section 2) of the study device with the reference rate with non-inferiority margin,  $\delta > 0$ :

$$H_0: \pi_0 - \pi \ge \delta$$
$$H_a: \pi_0 - \pi < \delta$$

Where  $\pi$  is success rate of study device and  $\pi_0$  is reference rate, respectively and  $\delta = 5\%$ . For these hypotheses, rejection of the null hypotheses will imply non-inferiority of the study device compared to the reference rate.

For the above hypotheses, the sample size for a specified  $\alpha$  and power  $(1 - \beta)$  is given by:

$$n = \frac{(z_a + z_b)^2 (\pi (1 - \mu))}{(\mu_0 - \mu - \delta)^2}$$

Where  $\delta$  is the non-inferiority margin and non-negative number [43].

The success rate for the study device is unknown for this population but there is no reason to believe that it would be less than reference rate of 93% (95%CI: 92.4-93.6%) [19]. Therefore, a conservative success rate of 93% of the study device is used at 10 years study.

The non-inferiority margin  $\delta$  of 0.05 is chosen in the study [43]. 225 subjects are required to achieve  $100(1 - \beta) \% = 80\%$  power to detect non-inferiority at the Significance level of  $\alpha = 0.05$  (single-sided hypothesis). Based on the experience, allowing 10% of the patients lost to follow up by the end of 10 years, a sample size of 250 cases are needed in this study. Therefore, 250 cases will be enrolled in the study (20 cases minimum to be recruited at each site; in case one centre is not able to recruit the allocated target size of cases, numbers can be picked up by the other centres).

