#### 3.1 Femoral Crush Fractures

A high prevalence of femoral crush-fractures were observed in Cohorts 1A and 2. Cohort 1A was followed up as per Figure 1 and recruitment of Cohort 2 commenced after the gateway safety analysis. The gateway safety analysis did not indicate any safety issues, but the 6 month safety data showed unexplained movement of the femoral head. As per procedure, recruitment for Cohort 2 was suspended and an investigation was launched in to the observed movement. The movement was found to be as a result of a femoral crush fracture. A thorough investigation was undertaken which concluded that

the root cause of the fracture was surgical technique, in particular post-operative femoral head centre. Upgrades have been made to the instrumented technique to eliminate these errors and the contoured rim of the implant has been modified to be more forgiving to implant placement error. A full report of the investigation is available on request.

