#### 8.3.3 All participants (Cohort 1A, Cohort 1B, Cohort 2)

In the safety and efficacy study the clinical and functional assessments will be done at 6 months and 7 years; and at 1, 2, 3, 5 and 10 years assessment of the clinical, functional and radiographic performance.

An interim analysis describing the safety and efficacy parameters is planned at 6 months and annually, and a final analysis will be done at 10 years. The interim analysis will consider the overall study population as well as the following pre-defined subgroups:

- Female Resurfacing Patients
- Patients implanted with a small femoral head diameter (Size 46 and below)
- Patients operated on pre- and post- the design upgrade

The interim analyses shall be independently reviewed by the Karolinska Institute in Stockholm, Sweden up to the 2 year interval.

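### The 80% power assumes 93% ten-year success across all 250 hips, yet the protocol reports a high prevalence of crush fractures in pre-upgrade hips that stay in the primary test

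*Protocol*

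**What the plan says.** Section 10.1.1 takes a literature reference rate of 93% at ten years and a non-inferiority margin "of 0.05 is chosen in the study", so the null boundary is 88%. The test is one-sided at 0.05 ("single-sided hypothesis"). On the device's own rate it states that "there is no reason to believe that it would be less than reference rate of 93" per cent, and concludes that "a conservative success rate of 93% of the study device is used at 10 years study". From this, "225 subjects are required to achieve" 80% power and, "allowing 10% of the patients lost to follow up by the end of 10 years, a sample size of 250 cases are needed".

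Section 3.1 states: "A high prevalence of femoral crush-fractures were observed in Cohorts 1A and 2". It goes on to say that Cohort 2 recruitment was suspended, that the root cause was found to be surgical technique, and that both the instrumented technique and the contoured rim of the implant were then changed. Section 8.1.1 adds Cohort 1B (46 patients) because of these fractures. Section 9.9 separates Cohort 2 into pre-upgrade and post-upgrade recruitment.

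Sections 9.8 and 10.1.1 count 250 cases in all and set none aside. Section 7.3.3 assigns implant survivorship to Cohorts 1A, 1B and 2, and Table 1 runs the ten-year final analysis on all three. The pre/post-upgrade comparison appears once, in section 8.3.3: "The interim analysis will consider the overall study population as well as the following pre-defined subgroups", and the third subgroup listed is the pre/post-upgrade one.

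**The concern.** The two sections disagree. Section 3.1 gives a reason to doubt 93% for an identifiable part of the sample, while section 10.1.1 says no such reason exists and treats 93% as a cautious choice. The trial was reorganised around the fractures, but the planning rate was not revisited.

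Two things are at stake. First, the stated 80% power applies to the pooled 250 only if the pre-upgrade hips also reach 93%. Second, the primary estimate mixes hips done with a superseded rim and technique with hips done after the change. The protocol says that the data will support a CE-marking submission, so readers of the final report will want to see the two groups separately at ten years. As written, the protocol promises that separation only at the interim looks.

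**Working it through.** **Inputs from section 10.1.1.** Reference 93%, margin 5 points, null boundary 0.93 − 0.05 = 0.88, one-sided α = 0.05, planned true rate 0.93, 225 evaluable, 10% loss, 250 enrolled.

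**Reproducing the plan's figure.** A one-sample test with the variance at 0.88 under the null and at 0.93 under the alternative gives

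n = [1.645 × √(0.88 × 0.12) + 0.842 × √(0.93 × 0.07)]² / 0.05² = 224.6, rounded up to 225; 225 / 0.90 = 250.

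So 225 and 250 both reproduce, and power at 225 is 80.1%. (With the variance taken only at 93%, as the printed formula appears to do, n is 161. That is a separate matter; the figures below use the version that returns the protocol's 225.)

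**How much slack there is.** Significance requires an observed rate above 0.88 + 1.645 × √(0.1056/225) = 0.9156, that is at least 207 successes or at most 18 failures in 225. At 93% the expected number of failures is 225 × 0.07 = 15.75.

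**Power at other true pooled rates, 225 evaluable.**

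Power(p) = Φ{[p − 0.88 − 1.645 × √(0.1056/225)] / √[p(1 − p)/225]}

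| True pooled rate | Power | Exact binomial |
|---|---|---|
| 93% | 80% | 77% |
| 92.5% | 70% | 67% |
| 92% | 60% | 56% |
| 91% | 38% | 35% |
| 90% | 22% | 19% |

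**Mixtures.** Let m be the number of pre-upgrade hips and S their ten-year success. Neither is given. Cohort 1A supplies 20, and the early part of Cohort 2 adds an unstated number. Assume 93% after the upgrade and equal loss to follow-up in both groups. Then pooled p = [m × S + (250 − m) × 0.93] / 250. For example, m = 20 and S = 0.80 give (16 + 213.9)/250 = 0.9196.

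| m | S | Pooled rate | Power |
|---|---|---|---|
| 20 | 90% | 92.8% | 76% |
| 20 | 85% | 92.4% | 67% |
| 20 | 80% | 92.0% | 59% |
| 40 | 90% | 92.5% | 71% |
| 40 | 85% | 91.7% | 53% |
| 40 | 80% | 90.9% | 37% |

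The step from 80% to 59% power corresponds to only 20 × (0.93 − 0.80) = 2.6 additional revisions among the 250 hips.

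**Post-upgrade hips alone, at 93%.** With 20 pre-upgrade hips, 230 × 0.90 = 207 evaluable gives 77% power. With 50, 200 × 0.90 = 180 evaluable gives 70%.

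**The case against.** The strongest reply is that a crush fracture is not the endpoint. The endpoint is revision, and section 3.1 gives no count of fractures, revisions or pre-upgrade hips. This stands: a reader might infer that the pre-upgrade hips will fall below 93%, or that power has dropped by a particular amount, and the protocol shows neither. The values of S above are assumptions, and at 90% in 20 hips the loss is only about four points. What does not stand is the claim that no reason for doubt exists. Section 8.1.3 counts revision for any cause and itself notes that the threshold for revising a resurfacing may be low.

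A second reply is that the upgrade removed the cause. That can support 93% for post-upgrade hips only.

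A third concerns the remedy. A reader might conclude that the primary test should be confined to post-upgrade hips. The documents do not support that. It would remove hips after their complications were seen, and in a single-arm comparison with a fixed rate this favours the device. It also recovers little power: with 20 pre-upgrade hips at 90%, power is 76% pooled and 77% post-upgrade only. Nor does pooling make a false claim of non-inferiority easier, since worse early hips make the test harder to pass. Keeping every hip is the cautious choice.

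A fourth is that the split is already pre-defined, with survivorship scheduled repeatedly, and that a statistical analysis plan, not available here, may carry it to year ten. That reduces the weight of this part of the point, but the protocol's own wording stops at the interim analyses.

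Finally, the lack of slack depends on the test. A Wald test with 225 evaluable would have 90% power at 93%, 72% at 92% and 47% at 91%. The sensitivity remains, from a higher starting point.

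**Conclusion.** The point holds as an internal contradiction in the power justification, together with a pre/post-upgrade split that the protocol ties only to interim analyses. The margin, α, null boundary and eventual estimate are unaffected. What fails is the assurance that 80% power applies to the pooled 250. Under the stated assumptions (225 evaluable, 93% after the upgrade, 20 to 40 pre-upgrade hips at 80 to 90%, null-variance test), power lies between about 76% and 37%. The documents do not allow a single figure. The severity is should-fix: correcting the text is cheap, and the risk is mainly to the trial's chance of showing non-inferiority and to how clearly its result can be read.

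**What to change.** - In section 10.1.1, delete the statement that nothing suggests a rate below the reference, and the description of 93% as conservative. Refer to section 3.1 instead.
- Restate power over a range of pooled ten-year rates, using the actual number of pre-upgrade hips and their revisions to date.
- State explicitly that all 250 hips remain in the primary non-inferiority test.
- In section 8.3.3, extend the pre/post-upgrade comparison to the final analysis. Prespecify the post-upgrade ten-year survivorship with its confidence interval, and the pre-upgrade estimate beside it, as supporting analyses. State the lower power of the post-upgrade set (about 77% with 207 evaluable, 70% with 180).

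The cost is revised wording and one more survival estimate in the final report, with no added patients. The drawback is that the stated power will look less favourable than 80%.

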#### 10.1.2 Secondary Objective - Safety Study

Regarding the safety analysis, the sample size is calculated based on the superiority of the ceramic-on-ceramic bearing couple compared to MoM hip resurfacings. Several studies [22] have demonstrated that ceramic bearings are not associated with metal ion release (levels below detection limits of most labs i.e. < 0.5 µg/L). Previous research [3] investigated metal ion measurements from well-functioning MoM unilateral hip resurfacings (n = 251) and found mean cobalt (Co) levels of 1.8 µg/L (median 1.5 µg/L – SD 1.2) and mean chromium levels of 2.0 µg/L (median 1.6 µg/L – SD 1.2). The Co and Cr levels of the ceramic-on-ceramic hips are expected to be < 0.5 µg/L. Thus 14 subjects in each group are required to achieve  $100(1 - \beta) \% = 80\%$  power to detect a difference in the mean Co levels at the Significance level of  $\alpha = 0.05$  (NCSS statistical software).

In order to account for patients lost to follow-up, unavailability or loss of blood samples or laboratory problems with measurements, 20 patients will be included in the metal ions investigation.

# 10.2 Statistical Analysis

A non-inferiority test of the cumulative percent success (defined in section 2) in subjects implanted with the H1 hip resurfacing compared to a literature reference rate will be the primary test of efficacy in this study. The null hypothesis is H0:  $\pi_0 - \pi \ge 0.05$  and the alternative hypothesis is Ha:  $\pi_0 - \pi < 0.05$ .

Primary and secondary outcomes will be evaluated using listings and summary statistics. A confidence interval of 95% will be calculated for proportions and averages. Improvement in pain and function will be analysed using parametric (t-test) or non-parametric (Wilcoxon Rank tests) as appropriate. A Kaplan Meier survival estimate will be calculated in this study. For the survivorship analyses, revisions are defined as revision for any reason. Prognostic factors will be adjusted, if necessary, using parametric or non-parametric analyses (log Rank; Cox regression). All statistical analyses and calculation of confidence intervals will be performed using appropriate statistical software packages.

#### 10.3 Missing data

In order to evaluate the potential impact of interim and final analyses, the reason of non-completed Patient Reported Outcome Measures Forms, or Radiographic Evaluation will be provided in the analysis reports. A complete accountability report, along with the explanation for lost-to-follow-up, death, revision, and withdrawn patients, is to be provided in the interim and final study analyses.

# **PART C:** PROCEDURES

# **11** Investigation procedures

The investigation procedures are summarised in Table 2 to Table 8.

Key:

- Blue indicates data for patient enrolment
- Green indicates baseline data
- Purple indicates data for clinical and functional outcomes
- Red indicates patient reported outcome measures
- Grey indicates data for radiological assessment
- Yellow indicates data for CT assessment
- Pink indicates data for toxicology
- Orange indicates data for complication rate

## Table 2. Schedule of procedures: Cohort 1A

			Ор							Post-op						
	Date	Pre-op	day	2days	6 wks	3 mos	6 mos	1 year	2 years	3 years	4 years	5 years	6 years	7 years	8,9 years	10 years
	Deviation window	≤4mos prior	0	±1day	±2wks	±2wks	±2wks	±2wks	±4wks	±4wks	±3mos	±3mos	±3mos	±3mos	±3mos	±3mos
	Informed consent	✓														
	Inclusions/exclusions	✓														
	Patient registration	✓														
	Medical history	~														
	Operative data		✓													
	Treadmill gait	~						~				~				
	Harris Hip Score	~			~	~	~	~	~	~		~		~		✓
	Oxford Hip score	✓			~	~	~	~	~	✓	✓	~	✓	~	✓	✓
ent	Imperial Hip Score	✓			~	~	~	~	~	~	✓	~	~	~	✓	✓
ssme	EQ-5D	✓			~	~	~	~	~	~	✓	~	~	~	✓	✓
Assessment	AP & Lateral Radiographs	✓ ≤12 mos prior		~						~		~				~
	Low dose CT scan Ultralow dose CT scan	~		~	~	、 ✓	~	✓	~							
	Metal ions questionnaire	~														
	Metal lons bloods	✓				~	~	~	~							
	Conmed questions	✓	✓	~	~	~	~	~	~	~	✓	~	~	~	~	✓
	Record Adverse Event	✓	✓	✓	✓	✓	✓	✓	✓	✓	✓	✓	✓	✓	✓	✓

## Table 3. Schedule of procedures: Cohort 1B

			Ор							Pos	t-op						
	Date	Pre-op	day	2days	6 wks	3 mos	6 mos	9 mos	1 year	2 years	3 years	4 years	5 years	6 years	7 years	8,9 years	10 years
	Deviation window	≤4mos prior	0	±1day	±2wks	±2wks	±2wks	±2wks	±2wks	±4wks	±4wks	±3mos	±3mos	±3mos	±3mos	±3mos	±3mos
	Informed consent	✓															
	Inclusions/exclusions	✓															
	Patient registration	✓															
	DXA scan	✓ ≤12 mos prior															
	Medical history	✓															
	Operative data		✓														
	Treadmill gait	✓							✓				✓				
	Harris Hip Score	✓			✓	✓	✓	✓	✓	✓	✓		✓		✓		✓
ent	Oxford Hip score	✓			✓	✓	✓	✓	✓	✓	✓	✓	✓	✓	✓	✓	✓
Assessment	Imperial Hip Score	✓			✓	✓	✓	✓	✓	✓	✓	✓	✓	✓	✓	✓	
 
✓
 

Asse	EQ-5D	✓			✓	✓	✓	✓	✓	✓	✓	✓	✓	✓	✓	✓	
 
✓
 

	AP & Lateral Radiographs	✓ ≤12 mos prior		~							~		~				~
	Low dose CT scan Ultralow dose CT scan	~		~	~	~	~	~	~	~							
	Metal ions questionnaire*	~															
	Metal Ions bloods*	✓				✓	✓		✓	✓							
	Conmed questions	✓	✓	✓	✓	✓	✓	✓	✓	✓	✓	✓	✓	✓	✓	✓	✓
	Record Adverse Event	✓	✓	✓	✓	✓	✓	✓	✓	✓	✓	✓	✓	✓	✓	✓	✓
*Me	tal ions questionnaire and	bloods only	taken f	or the firs	t 14 patie	ents in Co	hort 1B										

# Table 4. Schedule of procedures: Cohort 2 All sites (except \* which are UK sites only and \*\* which are online only)

	Date	Dro. or	Ор					Post-op				
	Date	Pre-op	day	2 days	6 weeks	6 months	1 year	2 years	3 years	5 years	7 years	10 years
	Deviation window	≤4 mos prior	0	±1 day	±2 weeks	±2 weeks	±2 weeks	±4 weeks	±4weeks	±3 months	±3 months	±3 months
	Informed consent	✓										
	Inclusions/exclusions	~										
	Patient registration	✓										
	DXA Scan	✓ ≤12 mos prior										
	Medical history	✓										
	Operative data		✓									
ent	Treadmill gait*	√*					√*			√*		
Assessment	Harris Hip Score	✓			✓	✓	✓	✓	✓	✓	✓	✓
Asse	Oxford Hip score	✓			✓	✓	✓	✓	✓	✓	✓	✓
	Imperial Hip Score**	√**			√**	√**	√**	√**	√**	√**	√**	√ **
	EQ-5D	✓			✓	✓	✓	✓	✓	✓	✓	✓
	AP & Lateral Radiographs	~		√	~		~	~	~	~		~
	Low dose CT scan*	<pre>✓* ≤12 mos prior</pre>										
	Conmed questions	~	✓	✓	✓	✓	✓	✓	✓	✓	✓	✓
	Record Adverse Event(s)	~	✓	✓	✓	✓	✓	✓	~	1	✓	✓

# Table 5. Schedule of procedures: Cohort 2 simultaneous bilateral patients – All sites (except \* which are UK sites only and \*\* which are online only)

		_						Post-op				
	Date	Pre-op	Op day	2 days	6 weeks	6 months	1 year	2 years	3 years	5 years	7 years	10 years
	Deviation window	≤4 mos prior	0	±1 day	±2 weeks	±2 weeks	±2 weeks	±4 weeks	±4weeks	±3 months	±3 months	±3 months
	Informed consent	✓										
	Inclusions/exclusions	√ √										
	Patient registration	√√										
	DXA Scan	✓ ≤12 mos prior										
	Medical history	√ √										
	Operative data		$\checkmark\checkmark$									
	Treadmill gait*	√*					√*			√*		
ient	Harris Hip Score	√ √			√√	√ √	√ √	√√	√√	√√	√ √	√√
Assessment	Oxford Hip score	√ √			$\checkmark\checkmark$	√ √	$\checkmark\checkmark$	√ √	$\checkmark\checkmark$	√ √	$\checkmark\checkmark$	$\checkmark\checkmark$
Asse	Imperial Hip Score**	√√**			√√**	√	√√ **	√√**	√√**	√√ **	√√ **	√√**
	EQ-5D	√ √			~~	√ √	√√	~~	√ √	~~	√ √	√ √
	AP Radiographs	✓ ≤12 mos prior		✓	✓		~	~	~	~		✓
	Lateral Radiographs	

✓✓ ≤12

mos prior

		~~	~~		√ √	~~	√ √	~~		√ √
	Low dose CT scan*	<pre>✓*^ ≤12 mos prior</pre>										
	Conmed questions	√ √	√ √	~ ~	~~	√ √	√√	~~	√ √	~~	√√	√ √
	Record Adverse Event(s)	vv	~ ~	~~	√ √	√ √	√ √	√ √	√√	√ √	√√	√√

 $\sqrt{4}$  = Separate assessments to be taken for both hips

### Table 6. Schedule of procedures: Staggered bilateral patient recruited from Cohort 1A into Cohort 2

	t Study Hip hort 1A)	Pre-op	Op day	2D	6 wks	3 mos	6 mos					1 year			2 years		3 years		4 years	5 years		6 years	7 years		8,9 years	10 years	
	tralateral Second dy Hip (Cohort 2)							Pre-op	OP Day	2 D	6 wks		6 mos	1 year		2 years		3 years			5 years			7 years			10 years
	Re-consent for contralateral Hip				1	1		 																			
	Inclusion/exclusion							 																			
	Patient registration							 																			
	DXA Scan							√^ ≤12 mos prior																			
	Medical History							 																			
	Operative data								 																		
ţ	Treadmill gait							 				✓		 						✓	 						
sme	Harris Hip Score	Ass	sessn		s don	e as	per	 			 	✓	 	 	✓	 	✓	 		✓	 		✓	 		✓	 
Assessment	Oxford Hip score			Tab	le 2			 			 	✓	 	 	✓	 	~	 	✓	✓	 	✓	✓	 	✓	✓	 
◄	Imperial Hip Score							 			 	✓	 	 	✓	 	~	 	✓	~	 	~	✓	 	✓	✓	 
	EQ-5D							 			 	✓	 	 	✓	 	~	 	✓	✓	 	✓	✓	 	✓	✓	 
	AP & Lateral Radiographs							√ ≤12 mos prior		 	 			 		 	~	 		~	 					~	~
	Ultra low dose CT											✓			✓												
	Metal Ions bloods											✓			✓												
	Conmed questions							 	 	√	 	✓	√	 	✓	 	~	 	✓	✓	 	✓	✓	 	✓	✓	 
	Record Adverse Event(s)							✓ ^- To be tak	 	~	~	✓	~	~	✓	~	~	 	~	~	 	~	~	 	~	~	~

✓ = First Study Hip

✓= Contralateral Second Hip

 $\underline{\checkmark \land}$  = To be taken only if previously DXA scan not done

#### 7 years 10 years 2 years years years Pre-op Op day 6 mos First Study Hip 6 wks year 2D (Cohort 2) ⊣ m ъ 10 years 7 years Op day 5 years **Contralateral second study Hip** Pre-op 2 year 6 mos 1 year 3 year 6 wks (Cohort 2) 2D Re-consent for $\checkmark$ contralateral Hip Inclusions/exclusions ✓ $\checkmark$ Patient registration ✓^ ≤12 mos DXA Scan prior Medical History ✓ Operative data ✓ Assessment Treadmill gait\* √\* √\* √\* √\* √\* Assessments done as per $\checkmark$ ✓ $\checkmark$ $\checkmark$ $\checkmark$ Harris Hip Score $\checkmark$ $\checkmark$ $\checkmark$ $\checkmark$ $\checkmark$ $\checkmark$ $\checkmark$ ✓ $\checkmark$ $\checkmark$ Table 4 ✓ ✓ $\checkmark$ $\checkmark$ $\checkmark$ $\checkmark$ $\checkmark$ ✓ ✓ $\checkmark$   Oxford Hip score $\checkmark$ $\checkmark$ ✓ $\checkmark$ **√**\*\* √\*\* **√**\*\* **√**\*\* **√**\*\* Imperial Hip Score\*\* √\*\* **√**\*\* **√**\*\* √\*\* **√**\*\* **√**\*\* √\*\* **√**\*\* √\*\* **√**\*\* $\checkmark$ EQ-5D $\checkmark$ ✓ $\checkmark$ $\checkmark$ $\checkmark$ $\checkmark$ ✓ ✓ $\checkmark$ $\checkmark$ ✓ ✓ $\checkmark$ ✓ √ ≤12 mos ✓ $\checkmark$ AP & lateral Radiographs $\checkmark$ ✓ $\checkmark$ $\checkmark$ $\checkmark$ $\checkmark$ ✓ $\checkmark$ prior √\* ≤12 mos Low dose CT scan\* prior ✓ **Conmed questions** $\checkmark$ $\checkmark$ ✓ $\checkmark$ $\checkmark$ $\checkmark$ ✓ $\checkmark$ $\checkmark$   $\checkmark$ $\checkmark$ ✓ ✓ $\checkmark$ ✓ ✓   Record Adverse Event(s) ✓ $\checkmark$ $\checkmark$ $\checkmark$ ✓ $\checkmark$ $\checkmark$ ✓ $\checkmark$ $\checkmark$ $\checkmark$ ✓ ✓ $\checkmark$

